7.4.1 Screening visit

All potential volunteers will have a screening visit, which may take place up to 42 days prior to vaccination. Informed consent will be taken before screening, as described in section 6.2. If consent is obtained, the procedures indicated in the Schedule of Procedures will be carried out. To avoid unnecessary additional venepuncture, if the appropriate blood test results for screening are available for the same volunteer from a screening visit for another Jenner Institute Clinical Trials group vaccine study, these results may be used for assessing eligibility (provided the result date is within the 42 days preceding enrolment in HIV-CORE 0052).

The subject's GP will be contacted with the written permission of the subject after screening to ascertain any significant medical history and as notification that the subject has volunteered for the study. The GP is not required to confirm the eligibility of the volunteer as this is solely assessed by the investigator on the basis of the medical history obtained. During screening, volunteers will be asked to provide their National Insurance or passport number so that this can be entered on to a national database which helps prevent volunteers from participating in more than one clinical trial simultaneously (www.tops.org.uk). Abnormal clinical findings from the urinalysis or blood tests at screening will be assessed as detailed in Appendix A. Abnormal blood tests following screening will be assessed according to site-specific laboratory AE grading tables which are filed in the trial master file (TMF). Any abnormal test result deemed clinically significant may be repeated to ensure it is not

a single occurrence. If an abnormal finding is deemed to be clinically significant, the volunteer will be informed and appropriate medical care arranged with the permission of the volunteer.

The eligibility of the volunteer will be reviewed at the end of the screening visit and again when all results from the screening visit have been considered. Decisions to exclude the volunteer from enrolling in the trial or to withdraw a volunteer from the trial will be at the discretion of the Investigator. If eligible, a day 0 (D0) visit will be scheduled for the volunteer to receive the vaccines and subsequent follow-up.

7.4.2 Day 0: Enrolment and vaccination visit

Volunteers will not be considered enrolled in the study until they have attended for their D0 visit. Before vaccination, the eligibility of the volunteer will be reviewed. Pulse, blood pressure and temperature will be observed and if necessary, a medical history and physical examination may be undertaken to determine any need to postpone vaccination/trial intervention depending on criteria listed in section 6.3.4. Blood, urine and faeces will be collected according to the Schedule of Procedures. HIV test and HIV test counselling will be performed. Volunteers will be recommended to take anti-pyretic medications before the booster vaccination (MVA.tHIVconsV3 and MVA.THIVconsV4) or soon after, if there is no clinical contra-indication. They should also be advised to take additional doses, as required, over the next 24-48 hours. Vaccination will be administered as described below.

7.4.2.1 Vaccination

All vaccines will be administered intramuscularly, in the deltoid region of each arm according to SOP VC002 Vaccination, as described below in section 8.4. The injection site will be covered with a sterile dressing and the volunteer will stay in the CCVTM for observation, in case of immediate AEs. Observations will be taken 30 minutes after vaccination (+/- 5 minutes), the sterile dressing removed and injection site inspected. For the first participant in each group, observations will be taken also 60 minutes after the first (C1) vaccination (+/- 5 minutes).

Participants will be given an oral thermometer, tape measure and login details for access to an electronic diary (e-diary) with instructions on use, to record solicited AEs, along with the emergency 24 hour telephone number to contact the on-call study physician if needed. Participants will be instructed on how to self-assess the severity of these AEs.

The e-diary will collect information on the timing and severity of the following solicited AEs:

Table 3. Solicited AEs as collected on post vaccination diary cards.

Local solicited AEs	Systemic solicited AEs
Pain	Fever
Redness	Feverishness/Chills
Warmth	Joint pains
Itch	Muscle pains
	Fatigue
	Headache
	Malaise
	Nausea

Participants will be instructed on how to self-assess the severity of these AEs. There will also be space to self-document unsolicited AEs, and whether medication was taken to relieve the symptoms.

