- Proportion of volunteers with local and systemic reactogenicity events from Day 0 to Day 6 post vaccination
- Proportion of volunteers with Grade 3 or 4 unsolicited adverse events (AEs) through 28 days post final vaccination
- Proportion of volunteers with vaccine related serious adverse events (SAEs) collected throughout the study period

SECONDARY

- Proportion of vaccine recipients developing HIV-1-specific T-cell responses
- Frequency, breadth and duration of the tHIVconsvX-specific T-cell responses to conserved epitopes measured in IFN- γ ELISpot assay in each vaccine recipient
- Breadth of inhibition of HIV-1 viruses *in vitro*

EXPLORATORY

- Proportions of mono-, bi- and tri-functional tHIVconsvX-specific T-cells in the vaccine recipients
- Shotgun sequencing and metabolomics analyses.

Investigational products

- The ChAdOx1.tHIVconsv1 vaccine utilises non-replicating engineered simian adenovirus vaccine vector ChAdOx1 to deliver a mosaic immunogen tHIVconsv1 derived from functionally conserved regions of HIV-1 proteins.
- Two vaccine components MVA.tHIVconsv3 and MVA.tHIVconsv4 complement each other and will be used as a pair for immunisations. They utilise non-replicating poxvirus MVA delivering bi-valent mosaic

immunogens, either tHIVconsV3 or tHIVconsV4, derived from functionally conserved regions of HIV-1 proteins.

Formulation Suspension (all finished products)

Route of Administration Intramuscularly (IM), into the deltoid region of each arm

Dose per Administration

- 5.0×10^9 vp of ChAdOx1.tHIVconsV1 (C1 low dose half a dose to be administered to each arm)
- 5.0×10^{10} vp of ChAdOx1.tHIVconsV1 (C1 high dose half a dose to be administered to each arm)
- 1.0×10^8 pfu of MVA.tHIVconsV3 (M3) left arm
- 0.9×10^8 pfu of MVA.tHIVconsV4 (M4) right arm

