5.6 Potential risks for volunteers

The potential risks are those associated with phlebotomy and vaccination.

- ***Venepuncture and intravenous cannulation***

The total volume of blood drawn per visit and over the four or five-month study period (less than 100ml for Group 1 participants or less than 600ml for Group 2 participants) is not expected to compromise volunteers' health. This is less than the volume allowed for both male and female blood donors over a similar period, therefore we do not anticipate AEs as a consequence of blood sampling. We will monitor for anaemia at regular intervals, as indicated in the Schedule of Procedures and participants will be asked to refrain from blood donation for the duration of their involvement in the trial.

Mild tenderness, bruising at the site of needle insertion, light-headedness, or rarely, syncope, may result from venepuncture. Study participants will be seated or reclining in order to minimise the risk of the latter.

- ***Allergic reactions***

Allergic reactions from mild to severe may occur in response to any constituent of a medicinal product's preparation. Anaphylaxis is extremely rare (less than 1 in 1,000 people) but can occur in response to any vaccine or medication. Advanced Life Support trained physicians, equipment and drugs are immediately available for the management of any serious adverse reactions (SAR).

- ***Vaccination***

- Local reaction from IM vaccination***

Typical local reactions as a result of IM injections are temporary pain, redness and swelling at the site of the injection.

- Systemic reactions***

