7.4.3 Subsequent visits

On subsequent visits, where specified in the Schedule of Procedures (section 7.1). Site personnel will:

- Review the e-diary and retain the information in the CRF
- Solicit and record local and systemic AEs
- Review and record interim medical history and concomitant medication
- Perform vital signs (pulse, blood pressure, temperature)
- Perform directed physical examination
- Assess the vaccination site
- Collect blood tests and faeces as specified in the Schedule of Procedures

7.4.4 *Final Visit*

The Final Visit or Early Termination Visit procedures will be performed according to the Schedule of Procedures (section 7.1). Site personnel will:

- Review any AEs and concomitant medications
- Perform vital signs (pulse, blood pressure and temperature)
- Perform a directed physical examination
- Assess any local and systemic reactogenicity events
- Collect blood and urine for tests as specified in the Schedule of Procedures
- HIV and STI screen and specific counselling as per Schedule of Procedure
- Perform a pregnancy test in all female volunteers where appropriate

7.4.5 *Unscheduled visits*

Visits/contacts other than those described in the Schedule of Procedures will be classified as unscheduled visits and recorded on a designated CRF. They may occur:

- For administrative reasons
- To review a laboratory investigation from a previous visit
- To review the outcome of an AE
- To conduct a study visit where a volunteer has missed the scheduled study visit window
- For any other reason requested by the volunteer or CI

7.4.6 *HIV testing and sexually transmitted infections (STI) Counselling*

Site personnel will counsel study participants about the implications of having blood tests for HIV, Hepatitis B, Hepatitis C and syphilis.

All volunteers will be assessed for HIV risk at screening, and tested for HIV antibodies as indicated in the Schedule of Procedures or as needed, if medical or social circumstances arise. All volunteers will receive HIV risk reduction counselling and pre- and post-HIV-test counselling, as specified below.

Trained and qualified study personnel will provide HIV counselling and testing at designated study visits as indicated in the Schedule of Procedures. Counselling will be provided in compliance with national guidelines.

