9.9 Safety Holding Rules

Safety holding rules have been developed considering the fact that this is a phase 1 study. Solicited AEs are those listed as foreseeable in the Investigator's Brochure for each product, occurring within the first 7 days after vaccination (day of vaccination and six subsequent days). 'Unsolicited AEs' are AEs other than the foreseeable AEs occurring within the first 28 days after vaccination.

9.9.1 *Re-vaccination excluding criteria*

The following AEs associated with vaccine immunisation constitute absolute contraindications to further administration of vaccine. If any of these events occur during the study, the subject must be withdrawn and followed until resolution of the event, as with any AE.

- Anaphylactic reaction following administration of the vaccine
- Pregnancy

The following AEs constitute contraindications to administration of vaccine at that point in time; if any one of these AEs occurs at the time scheduled for vaccination, the subject may be vaccinated at

a later date, or withdrawn at the discretion of the CI. The subject must be followed until resolution of the event as with any AE.

- Acute disease at the time of vaccination (defined as the presence of a moderate or severe illness with or without fever). All vaccines can be administered to persons with a minor illness such as diarrhoea, mild upper respiratory infection with or without low-grade febrile illness, i.e. temperature of $< 37.7^{\circ}\text{C} / 99.9^{\circ}\text{F}$.
- Temperature of $\geq 37.7^{\circ}\text{C} (99.9^{\circ}\text{F})$ at the time of vaccination.

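### Swelling is named as a typical local reaction but has no e-diary prompt, so its capture and its counting in the primary reactogenicity endpoint are not assured

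*Combined protocol and SAP*

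**What the plan says.** Section 5.6 says of local reactions: "Typical local reactions as a result of IM injections are temporary pain, redness and swelling at the site of the injection".

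Section 7.4.2.1 gives each volunteer a thermometer, a tape measure and access to an e-diary, and says "The e-diary will collect information on the timing and severity of the following solicited AEs". The list, titled "Table 3. Solicited AEs as collected on post vaccination diary cards", has four local items (pain, redness, warmth, itch) and eight systemic items. Swelling is in neither column, and no other section adds it to the diary. For anything else, the same section says: "There will also be space to self-document unsolicited AEs, and whether medication was taken to relieve the symptoms".

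Section 9.9 defines the same term from another source: "Solicited AEs are those listed as foreseeable in the Investigator's Brochure for each product, occurring within the first 7 days after vaccination". Other events in the first 28 days are unsolicited.

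The first primary endpoint in the Synopsis is "Proportion of volunteers with local and systemic reactogenicity events from Day 0 to Day 6 post vaccination". Neither the Synopsis nor the table in Section 4 lists its component events or ties it to Table 3. The second primary endpoint counts unsolicited events only at Grade 3 or 4.

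At later visits, where the Schedule of Procedures calls for it, staff are to "Solicit and record local and systemic AEs" and to assess the vaccination site (Section 7.4.3).

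**The concern.** The protocol prompts daily for two of the three local reactions that it calls typical and leaves out the third. It prompts instead for two (warmth, itch) that Section 5.6 does not name. An event that is asked about each day is recorded more completely than one that the volunteer must think to write down.

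Local reactogenicity is part of the first primary endpoint, and Section 10 takes the incidence of mild, moderate or severe events as the measure of safety, so low-grade events matter. The reported event profile also feeds the safety reviews that govern staggered enrolment (Section 5.2.1). What is not prompted for in the first week cannot be reliably recovered later.

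**Working it through.** **1. The two lists side by side.**

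| Local event | Named as typical in 5.6 | Solicited in Table 3 |
|---|---|---|
| Pain | yes | yes |
| Redness | yes | yes |
| Swelling | yes | no |
| Warmth | no | yes |
| Itch | no | yes |

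Table 3 reads as complete. A row lost when the PDF was converted to text cannot be fully excluded, so the original page should be checked.

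**2. The other routes by which swelling can be recorded.**

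- Diary free text (7.4.2.1): available, but described as a space for unsolicited events and without a prompt.
- Staff questioning and site assessment (7.4.3): the reactogenicity assessment is scheduled at D0 and D7 in Group 1, and at D0, D1, D7, D28, D29 and D35 in Group 2 (Tables 2a and 2b). The post-injection check on D0 is at about 30 minutes. The D7 visit has a window of ±3 days, so it can fall as early as 7 − 3 = D4. Within Day 0 to Day 6, D2 and D3 therefore always lie between scheduled visits, while D4 to D6 may or may not. Apart from Table 3, the protocol gives no list of items for staff to ask about.
- General recording (9.4): all local events in the 28 days after each vaccination, if observed by staff or reported by the volunteer. This adds no prompt.

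Swelling that appears and resolves between visits thus reaches the record through free text or through recall at the next visit.

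**3. How recorded swelling would be classed within the first week.**

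| List that governs | Class of swelling | Grade 1-2 | Grade 3-4 |
|---|---|---|---|
| Table 3 | unsolicited | outside the Grade 3/4 endpoint; in reactogenicity only if that endpoint is wider than the solicited items | counts as unsolicited Grade 3/4 |
| 9.9, Brochure lists swelling | solicited | counts as reactogenicity | counts as reactogenicity |
| 9.9, Brochure does not list it | unsolicited | as in the first row | counts as unsolicited Grade 3/4 |

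The Brochure is not among the documents, so the second and third rows cannot be told apart. In the first and third, Grade 1-2 swelling may enter neither endpoint.

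**4. Size.** The plan gives no figure to reproduce. Section 10 justifies the total of 3 + 10 = 13 by feasibility and states no precision. Section 10 does not say whether proportions are pooled or by group, so the weight of one missed volunteer, 100/n, is shown for each:

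- n = 3: 33.3 points
- n = 10: 10.0 points
- n = 13: 7.7 points

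Exact (Clopper-Pearson) 95% intervals for swelling as an individual sign, with none or one observed:

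- n = 10: 0/10 gives 0 to 30.8%; 1/10 gives 0.3 to 44.5%
- n = 13: 0/13 gives 0 to 24.7%; 1/13 gives 0.2 to 36.0%

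A proportion with any local reaction loses a volunteer only if swelling was that volunteer's sole local event and no other route counted it. With p the swelling rate and s the share in whom it is the sole local event, the expected loss is n × p × s. The documents give neither rate. As an assumption, take p from 5% to 30% and s from 0 to 25%, and let every sole-swelling case be lost:

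- Lower end (s = 0): 0 volunteers.
- Upper end, n = 13: 13 × 0.30 × 0.25 = 0.975 volunteers, and P(at least one lost) = 1 − (1 − 0.075)^13 = 0.64.
- Upper end, n = 10: 10 × 0.30 × 0.25 = 0.75 volunteers, and P(at least one lost) = 1 − (1 − 0.075)^10 = 0.54.

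The effect on the composite therefore runs from none to about one volunteer.

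**The case against.** The strongest case against is that the protocol does not rely on the diary alone. Nothing confines the primary endpoint to Table 3. Staff question volunteers about local events and look at the site, a D7 visit follows in both groups, a D35 visit follows the boost, and every local event reported within 28 days is recorded. The trial has 13 volunteers and a mainly descriptive safety analysis, so no test or error rate is affected.

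All of this stands, and it rules out three stronger readings that a reader might infer:

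- *That the primary endpoint does under-count swelling.* The documents show only that its capture and counting are not assured. No sourced incidence or capture rate exists from which to estimate a number missed, and the staff questioning tells against assuming wholly unprompted capture.
- *That the site goes unseen on all of D2 to D6.* This holds at nominal visit days only; the window can bring the D7 visit forward to D4.
- *That a Grade 3 swelling could fall outside both primary endpoints.* Under Section 9.9 a recorded event in the first week is either solicited or unsolicited. It would escape both counts only if one list were used for one endpoint and the other list for the other, which no section prescribes.

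The objection does not remove the inconsistency. One recall question at about D7 is weaker than a daily prompt, and no section says how swelling recorded by another route is counted.

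**Conclusion.** The omission is a fact of the text: swelling is typical in Section 5.6 and absent from Table 3, and Section 9.9 points to a second list. The consequence is a risk, not a demonstrated bias. Swelling as an individual sign may be under-ascertained, and low-grade swelling entered as unsolicited may count in neither of the two primary endpoints concerned. Each missed volunteer shifts the swelling proportion by 10 points at n=10 and 7.7 points at n=13. The proportion with any local reaction may change little or not at all; the figure of at most about one volunteer in 13 rests on assumed rates. The conclusion assumes that Table 3 is complete as read, and it does not depend on what the Brochure lists.

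**What to change.** Add swelling to the local column of Table 3 and to the e-diary, recorded as the largest diameter measured with the tape already supplied and graded on the severity scale adopted in Section 9.5. State with the primary endpoint that swelling recorded by any route from Day 0 to Day 6 counts as a local reactogenicity event. If the omission is deliberate, say so and say where swelling is counted.

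Reconcile Section 7.4.2.1 with Section 9.9 on which list defines a solicited event. Section 9.9 sits with the holding rules, and Section 9.10.2 has a halt criterion based on unforeseen severe events. The edit should therefore settle the data-collection list only and leave the meaning of unforeseen in that criterion as it is.

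The cost is one diary field, one table row and one or two sentences. Reported local reactogenicity may come out slightly higher.

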7.4.3 Subsequent visits

On subsequent visits, where specified in the Schedule of Procedures (section 7.1). Site personnel will:

- Review the e-diary and retain the information in the CRF
- Solicit and record local and systemic AEs
- Review and record interim medical history and concomitant medication
- Perform vital signs (pulse, blood pressure, temperature)
- Perform directed physical examination
- Assess the vaccination site
- Collect blood tests and faeces as specified in the Schedule of Procedures

7.4.4 *Final Visit*

The Final Visit or Early Termination Visit procedures will be performed according to the Schedule of Procedures (section 7.1). Site personnel will:

- Review any AEs and concomitant medications
- Perform vital signs (pulse, blood pressure and temperature)
- Perform a directed physical examination
- Assess any local and systemic reactogenicity events
- Collect blood and urine for tests as specified in the Schedule of Procedures
- HIV and STI screen and specific counselling as per Schedule of Procedure
- Perform a pregnancy test in all female volunteers where appropriate

7.4.5 *Unscheduled visits*

Visits/contacts other than those described in the Schedule of Procedures will be classified as unscheduled visits and recorded on a designated CRF. They may occur:

- For administrative reasons
- To review a laboratory investigation from a previous visit
- To review the outcome of an AE
- To conduct a study visit where a volunteer has missed the scheduled study visit window
- For any other reason requested by the volunteer or CI

7.4.6 *HIV testing and sexually transmitted infections (STI) Counselling*

Site personnel will counsel study participants about the implications of having blood tests for HIV, Hepatitis B, Hepatitis C and syphilis.

All volunteers will be assessed for HIV risk at screening, and tested for HIV antibodies as indicated in the Schedule of Procedures or as needed, if medical or social circumstances arise. All volunteers will receive HIV risk reduction counselling and pre- and post-HIV-test counselling, as specified below.

Trained and qualified study personnel will provide HIV counselling and testing at designated study visits as indicated in the Schedule of Procedures. Counselling will be provided in compliance with national guidelines.

The counselling process will, at a minimum, include information on HIV, safe sex practices and risk reduction. The objective of counselling is to ensure that volunteers have sufficient knowledge about HIV infection to understand what the test is for, the implications of a positive or negative result and the care available for HIV infection locally. Additionally, risk reduction counselling, safe sex practices, proven methods of preventing HIV acquisition and avoidance of transmission to others will be discussed with all volunteers regardless of their HIV test results.

Volunteers who are infected with HIV at screening and during follow up will be counselled and referred for care and treatment as needed. Counselling for HIV infected volunteers will include:

- Psychological and social implications of HIV infection
- Implications for sexual partners and family members
- Implications for child-bearing
- Avoidance of transmission to others in future
- Where to obtain HIV counselling, care and treatment

